6.6 Safety Assessments

Measurement of all safety parameters should be performed as described in Table 3. Adverse event reporting is discussed in detail in Section 7.

Standardized instructions for determining all other safety parameters are provided in the following sections.

6.6.1 Prior and Concomitant Medication and Treatment

Concomitant medications will be recorded at all study visits. All pharmacologic (including, but not limited to opioids, NSAIDs, aniline analgesics, tricyclic antidepressants and membrane stabilizers/anticonvulsants) and non-pharmacologic treatment used by study subjects within 6 months prior to screening should be recorded. Any dose modification of concomitant medications should be checked at each visit and recorded. Pain medication, specifically opioids and non-opioids (e.g. NSAIDS and aniline analgesics), usage will also be recorded by the subject into an e-diary to determine actual pain medication usage over a 2-week period during screening and prior to each in-clinic visit.

All subjects will be asked to enter pain medication (e.g. opioid, NSAID and aniline analgesics) usage information into an e-diary during screening. For baseline assessment of pain medication use, subjects should complete pain medication e-diaries for 2 weeks prior to any screening injection procedures (i.e., diagnostic disc injection to confirm intact annulus or discography, medial branch block and SI joint injection, if deemed necessary). If a subject had received a previous diagnostic injection procedure to confirm intact annulus or discography prior to the screening period (but within the permitted timeframes to serve as the baseline evaluation; see Section 4.2.2), the 14-day e-diary must be started at least 14 days after that injection procedure. If more than 4 out of 14 daily entries are missing, the subjects should be asked to continue completing the e-diary until 10 out of 14 daily entries are obtained. Following study treatment, subjects should complete the pain medication e-diary every day for a 2 week period during the 30 days prior to each clinic visit, other than the 1 month visit that must be conducted within the 14 days prior to the 1 month visit using electronic diaries (e-diaries) completed by the subjects. At each clinic visit at least 10 of 14 daily entries should be available. The site is to review the pain medication reported and log the visit within the subject's e-diary to close the reporting for that visit.

6.6.2 **Post-treatment Interventions at the Treated Level**

Surgical and injection interventions should be avoided through at least the 24 month primary endpoint follow-up. Surgical and injection interventions should only be undertaken if the subject's pain, measured by VAS, and function, measured by ODI, is not improved compared to the baseline values since an intervention could confound the efficacy assessments and would classify a subject as a treatment failure.

Records of secondary interventions during the post-treatment period are collected in this study for use in efficacy and safety analyses. As a safety measure, subjects requiring post-treatment interventions may be monitored for newly occurring AEs, and other concomitant treatments received in the same period of time. Post-treatment interventions will be adjudicated by a blinded and independent TEC. Following are procedures that should be considered interventions and consequently treatment failures for responder analyses if they occur at the treated level:

Surgical Interventions

- Spine fusion, interbody or posterolateral
- Artificial Disc Replacement
- Interlaminar or Spinous Process Stabilization Device Implantation

- Discectomy
- Surgical Disc Decompression, including minimally invasive decompression procedures such as mild®
- Laminectomy
- Laminotomy
- Osteotomy
- Foraminotomy
- Facetectomy
- Facet Joint Ablation/Denervation/Rhizotomy
- Disc nucleoplasty
- Spinal cord stimulation
- Intradiscal Electrothermal Annuloplasty
- Intradiscal Ablation Procedures
- Intrathecal pump implantation.

Spine Injections

- Epidural steroid injections
- Transforaminal injection of corticosteroid
- Injection of any anesthetic, analgesic, steroid or other potential pain relieving substance into the disc
- Facet Injection of corticosteroid.

For any subjects who are planning a post-treatment intervention during the course of the study, every effort should be made to schedule an "unscheduled visit" within a 30-day time window prior to the intervention. However, if the subject's originally scheduled visit falls within 30 days prior to the planned intervention, the unscheduled visit will not be necessary.

6.6.3 Neurological Examination

Neurological examination will be performed at screening and at each scheduled study visit thereafter. During screening, the neurological exam will be performed twice: once at any time during the screening period prior to the diagnostic injection to confirm an intact annulus or discography, and once after the diagnostic injection, prior to discharge, to assess if the injection procedure has resulted in any neurologic changes. If a historical diagnostic injection to confirm an intact annulus is used, the neurologic exam prior to the injection can be waived. In this case, the neurological exam will be performed during the screening period and will be used as the subject's baseline neurological exam for inclusion/exclusion determination as well as comparing to follow-up visits for any changes from baseline. The neurological exam prior to the diagnostic injection to confirm an intact annulus or discography, as well as the neurologic exam prior to the treatment injection, will be performed by either the unblinded or blinded evaluator, but preferably by the blinded evaluator who is to perform neurological exams from Visit 3 through the duration of the study. The post-diagnostic injection exam will be performed by the health care professional performing the injection procedure; this person may or may not be blinded.

Additionally, a neurological examination is to be performed after the treatment injection at Visit 2, prior to discharge, to assess if the injection procedure has resulted in any neurologic changes. This examination is to be performed by the unblinded health care professional performing the injection procedure to avoid the potential unblinding of the blinded evaluator.

The neurologic exam should include an assessment of lumbar-associated motor function, reflexes and sensory functions at L1-S1 and will assist in determination of adverse events.

The neurological evaluation must be conducted by the investigator or by a qualified medical practitioner delegated by the investigator. The components of the exam are:

Motor (Muscle Strength)

Each of the following assessments will be performed on the left and right side:

- Hip flexion
- Knee flexion
- Knee extension
- Ankle dorsiflexion
- Ankle plantar flexion
- Great toe dorsiflexion.

Subjects will receive a grade for each assessment performed (e.g., a grade for the left-sided hip flexion and a grade for the right-sided hip flexion). The grading system is as follows:

- 0 = no movement
- 1 = trace of muscle contraction
- 2 = active movement without gravity
- 3 =active movement against gravity
- 4 = active movement against resistance

A subject who receives a grade of 4 for all assessments will be considered a success for the motor exam. All other subjects will be considered failures for the motor exam. A failed baseline motor exam at any location would exclude the subject.

Sensory Exam of Dermatome Distribution:

Using a pinwheel, the clinician will evaluate both left and right dermatomes at each of the following levels:

- Hip Girdle and Groin Area (L1)
- Mid-anterior Thigh (L2)
- Medial Femoral Condyle (L3)
- Medial Malleolus (L4)
- Dorsum 3rd MTP Joint (L5)
- Lateral Heel (S1).

Subjects will be assessed as pass/fail for the sensory exam. A subject who experiences sensation in response to the pinwheel stimulus at each of the dermatomes will be considered a success for the sensory exam; all other subjects will be considered failures for the sensory exam. A failed baseline sensory exam at any dermatome would exclude the subject

Patellar and Ankle Reflex Exam:

- Patellar: subject is seated on a table with legs hanging at the knee. The clinician administers a patellar reflex response test 3 times on both the left and right side.
- Ankle: subject is seated similar to the patellar reflex exam. The clinician dorsiflexes the ankle to put tension on the Achilles tendon, then administers an ankle reflex response test 3 times on both the left and right sides.

If a subject experiences at least one reflex response for both the left and right side on both the patellar and ankle reflex response exams, that subject will be considered a success for the reflex exam. All other subjects will be considered as failures for the reflex exam. A failed baseline reflex exam for either patellar or ankle reflex would exclude the subject.

Subjects will also be asked if they have experienced other neurological symptoms and will be observed for foot drop or other gait disturbances. Affirmative responses or positive observations should be reported as adverse events.

6.6.4 Disease-targeted, Abbreviated Physical Examination

A disease targeted/abbreviated physical examination including, but not limited to, examination of the musculoskeletal system will be performed at screening. Abbreviated, symptom-driven physical examinations noting any adverse changes or new adverse findings since baseline as adverse events will be performed at each subsequent evaluation through the course of the study (Day 0 and 1, 3, 6, 12, 18, 24 and 36 months post-treatment). Exams must be performed by qualified healthcare personnel.

6.6.5 Vital Signs

Vital signs will be recorded at screening, at Day 0 pre- and post-treatment, and at 1, 3, 6, 12, 18, 24 and 36 months post-treatment.

Vital signs will include sitting (if possible) blood pressure, heart rate per minute and oral temperature.

On the day of the treatment injection, these should be performed prior to the procedure and then following the procedure, prior to discharge. Vital sign measurements will be taken at every visit.

6.6.6 Height and Weight

Height, weight, and BMI measurements will be performed at screening, at Day 0 and 1, 3, 6, 12, 18, 24 and 36 months post-treatment.

6.6.7 MRI Scans and X-rays

MRI scans will be performed at screening and at 12, 18, 24 and 36 months post treatment. Flexion/extension X-rays and AP, lateral X-rays will be performed at screening, 1, 3, 6, 12, 18, 24 and 36 months. MRIs and X-ray scans should be taken on the same machine using the same settings, and in accordance with the radiographic guidelines provided, from baseline to completion of the study to minimize potential differences in results caused by use of different machines. Radiographic evaluations may vary for a given subject depending on the time of day the assessments are made. Therefore, for each subject, all radiographic evaluations of a specific type (e.g., X-ray or MRI) should be taken at the same time of day at each assessment if possible, preferably in the morning.

Radiographic images (MRI and X-rays) will be sent to the imaging core lab for blinded, independent radiographic evaluation. Review of radiographic images will be conducted by two blinded independent radiologists with a third reviewer to adjudicate any differences between the reviewers. Review of the radiographic images for the criteria specified in the inclusion/exclusion to be conducted by the radiographic core lab will be conducted by two reviewers with a third reviewer to adjudicate any differences. The MRI and X-ray scans will be used for efficacy assessments. Investigators should also evaluate images for potential safety issues, such as disc herniation, worsening disc morphology, heterotopic ossification (osteophytes), annular tears/fissures and/or changes in bony structures. The radiographic evaluations to be conducted are included in Appendix 1.

Investigators will review the radiographic imaging provided on-site or locally, as well as any associated reports. The investigator should document his or her review, including any clinically significant findings. In addition, radiographic imaging reports for screening will be made available to the investigator from the core imaging provider. Investigators should review such reports and maintain documentation of the review and any clinically significant findings. Radiographic imaging and reports should be kept as part of the subject's medical record.

As differences in readings between investigators and the core imaging provider are expected, reconciliation between imaging assessments will not be necessary. Throughout the course of the study, radiographic efficacy endpoints will be based on results from the core imaging provider. The investigator reviews will be used to determine any potential safety issues (including AEs).

Section 6.7.4 provides further discussion of the radiographic efficacy endpoints.

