1.7.5 Effects on Treated and Adjacent Levels

It is unknown at this time what the long-term effects of injection of rexlemestrocel-L are. There is the potential that over the longer-term, adverse effects on the disc or adjacent vertebral bodies, such as osteolysis or Schmorl's nodes, could develop. Through 24 months, no significant adverse effects on the treated disc or surrounding structures, such as the adjacent vertebral bodies or neurologic structures, were observed in the Phase 2 clinical study.

It is unknown what if any effects injection of rexlemestrocel-L, hyaluronic acid or any other substance may have on adjacent level(s). Although, no significant changes in the adjacent levels after injection of rexlemestrocel-L with hyaluronic acid in the Phase 2 study were seen.

Adverse effects on the disc or adjacent vertebral bodies of the treated or adjacent levels could cause additional or recurrent pain and reduced function that could require treatment through medication and/or interventional procedures such as additional injections or surgery to correct the degeneration of the index or adjacent level(s).

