6.1.3 Safety and Efficacy Evaluation Period (Day 0 to 24 Months Post-treatment)

On Day 0/Treatment Administration day, each subject will receive an intradiscal injection of rexlemestrocel-L alone, rexlemestrocel-L +HA, or saline control in a 1:1:1 randomization ratio. This will commence the 24-month primary safety and efficacy period, which includes intensive safety and efficacy evaluations.

Treatment injection and post-procedure care (anesthesia, prophylactic antibiotics, blood product [i.e., packed red blood cells and platelets], rehabilitation regimens, etc.) will be performed in accordance with standard of care, as appropriate in the judgment of the investigator, and documented.

Subjects will be given the following directions for post-injection rehabilitation/treatment:

- Day of Procedure Bed Rest
- Day After Procedure Gentle Ambulation with gradual increase thereafter
- Days 1 to 3 Avoid repetitive bending, stooping and lifting greater than 10-15 lbs.
- Return to normal daily activity when pain has subsided to their baseline.

After the treatment injection visit, all safety and efficacy evaluations should be completed by blinded site staff.

Subjects will attend study visits 3, 4, 5, 6, 7, and 8 (corresponding to 1, 3, 6, 12, 18 and 24 months post-treatment) to complete the primary safety and efficacy period. Subjects will return at Study Visit 9 for a 36 month long-term safety and efficacy evaluation before completing the study. Subjects may also attend unscheduled visits for safety reasons as warranted.

If, for any reason, additional medication must be prescribed, subjects should inform the study site personnel.

Subjects may call the investigator at any time during the study if they experience any problems. The investigator may decide to follow up with a telephone call and/or request an unscheduled visit.

At least 2 blinded independent radiologists with a third radiologist to adjudicate any differences between two initial radiographic reviewers' assessments will review the specified screening radiographic images to confirm subjects meet the radiographic inclusion/exclusion criteria. Follow-up evaluation of radiographic images and any screening assessments that are not inclusion/exclusion criteria will be performed by at least 2 blinded independent radiologists with a third radiologist to adjudicate any differences between two initial radiographic reviewers' assessments as specified in Appendix 1.

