9.7.1 Primary Safety Endpoint

Evaluation of overall safety, which includes the following:

- Subject reported AEs and SAEs from baseline through 24 months post-treatment, including adverse events of special interest (i.e., AEs of worsening low back pain)
- Laboratory tests (hematology, serum chemistry, inflammatory markers and antibody analysis). Abnormal results will be assessed relative to normative ranges and shift tables from baseline through 24 months post-treatment
- Reported events from radiographic imaging from baseline through 24 months posttreatment, including disc height at the treated level
- Post-treatment interventions affecting the treated disc through Visit 8 (24 months posttreatment) (comparison of the proportion of subjects in each group with an adjudicated post-treatment intervention at the treated level, and the proportion of subjects in each group with an adjudicated post-treatment intervention any lumbar level)
- Vital signs (heart rate, blood pressure and temperature) and body measurements (height, weight and BMI)
- Physical examinations (abbreviated).
- Neurological examinations (motor, sensory, reflex).

[figure not shown]
Descriptive statistics will be used for the summary of safety parameters – the number and percentage will be used for the incidences of AE/SAEs, deaths, early discontinuation due to AEs, and post-treatment interventions. The AE/SAE severity and relationship with the study procedure and treatment will be summarized and presented.

The mean, standard deviation/error, minimum, median, and maximum will be used for the laboratory parameters. The shift table (cross-tabulation) for the changes from baseline (low/normal/high) for the laboratory parameters will also be also provided and the test for treatment difference.

[figure not shown]
Safety parameters of special interest (i.e., AEs of worsening low back pain) will be summarized through 24 months post-treatment by treatment arm, severity, and the time from the study injection to the start of the AEs (0 to \leq 7 days, >7 days to < 3 months, \geq 3 months to 24 Months).

The incidence of this special interest AE (worsening low back pain) occurring within 3 to 24 months after study treatment will be also summarized, by treatment arm, for the responders and non-responders of the Primary Efficacy Endpoint.

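### Imaging adverse events come from site reads with reconciliation waived; apart from disc height, the readable text brings no core-lab structural finding into the safety evaluation

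*Combined protocol and SAP*

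**What the plan says.** All study scans are read centrally: "Radiographic images (MRI and X-rays) will be sent to the imaging core lab for blinded, independent radiographic evaluation" (6.6.7). Section 6.1.3 gives the number of readers: "Follow-up evaluation of radiographic images and any screening assessments that are not inclusion/exclusion criteria will be performed by at least 2 blinded independent radiologists". Another reader settles differences, and the scope is left to Appendix 1.

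Investigators review the same imaging locally. Section 6.6.7 asks them to look for safety issues and gives examples: herniation, worsening disc morphology, heterotopic ossification, annular tears and bony change.

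The protocol expects the two sets of reads to differ and says that "reconciliation between imaging assessments will not be necessary". It then assigns each a use. For the core lab, "radiographic efficacy endpoints will be based on results from the core imaging provider". For the site, "The investigator reviews will be used to determine any potential safety issues (including AEs").

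On what returns to the site, 6.6.7 says that "radiographic imaging reports for screening will be made available to the investigator from the core imaging provider". For follow-up, 6.7.4 gives the investigator the images and mentions no core-lab report.

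The primary safety endpoint in 9.7.1 includes "Reported events from radiographic imaging from baseline through 24 months" post-treatment, and the same item adds disc height at the treated level. It does not say whose read supplies these events.

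**The concern.** Section 1.7.5 says the long-term effects of the injection are unknown and allows for "adverse effects on the disc or adjacent vertebral bodies, such as osteolysis" and Schmorl's nodes. Section 1.7.8 cites a 10-year matched cohort in which punctured and injected discs degenerated and herniated more than control discs. Structural change on imaging is therefore a harm the protocol itself anticipates.

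For consistency and to limit bias, the protocol relies on independent blinded readers (5.5, 3.1). Yet it determines imaging adverse events from the reviews of investigators at up to 45 sites. If a core-lab reader records a worse disc at follow-up and the site does not, the readable text states no way for that finding to be assessed as an adverse event or, disc height aside, to be counted as safety data. The comparison of structural harm between arms would then rest on the less standardised of two available sources.

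**Working it through.** The protocol gives no figure to reproduce. The check traces the two sets of reads from scan to analysis.

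| | Investigator review | Core lab |
|---|---|---|
| Reader at follow-up | Investigator, with local imaging and any associated reports (6.6.7); up to 45 sites (3.3) | At least two blinded radiologists plus an adjudicator (6.1.3) |
| Findings named for follow-up | Herniation, worsening morphology, ossification, annular tears, bony change (6.6.7) | Modified Pfirrmann score, disc height, stability index, and T1 rho/T2 mapping in a subset (6.7.4); Appendix 1 not readable |
| Stated use | Potential safety issues and adverse events (6.6.7) | Radiographic efficacy endpoints (6.6.7); disc height is also named in 9.7.1 |
| Destination | Documented in source (6.7.4) and reported if an adverse event | Sent directly to the sponsor or designee (10.4); reports to the site stated for screening only (6.6.7) |

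1. The assignment of safety to the investigator and the waiver of reconciliation are explicit. They are not inferred from silence.
2. The absence of a follow-up report to the site is inferred. The text limits its statement to screening and does not forbid more.
3. Disc height is the exception. Section 9.7.1 puts it in the safety endpoint, and 6.7.4 describes it among evaluations for which all imaging goes to the core lab. No reader is named in 9.7.1, so this attribution is probable rather than stated.
4. Section 6.7.4 has the treated and adjacent discs scored on the modified Pfirrmann scale and describes this as an assessment of improvement. The same scores would show worsening, but no readable safety analysis uses them.
5. Later safeguards do not clearly close the gap. The Treatment Events Committee adjudicates the relatedness of adverse events (12.2), so a finding never reported as one does not reach it by that route. The unblinded DSMB reviews safety reports and study findings (12.1), but core-lab imaging is not named.

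**Size.** The following figures are assumptions, used only to show why no size can be stated. Take a 5% incidence in an arm of 120: 0.05 × 120 = 6 events. With site sensitivity of 50% to 80%, 3.0 to 4.8 are counted. Add a core-lab read at 80% sensitivity:

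- Independent misses: 1 − (1 − 0.5)(1 − 0.8) = 0.90, or 5.4 events; 1 − (1 − 0.8)(1 − 0.8) = 0.96, or 5.76 events.
- Fully overlapping detection: 0.80 in both cases, or 4.8 events.

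The gain runs from 4.8 − 4.8 = 0 to 5.4 − 3.0 = 2.4 events per arm. It is also zero for any finding the core lab does not read. No input except the arm size of about 120 comes from the documents, so this range is not an estimate.

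**The case against.** The strongest reply is that the split is deliberate. Section 6.6.7 expects differences between readers, gives central reads to efficacy, and leaves safety with the clinician who knows the patient. Investigators must examine the same images, so a harm is lost only if the site misses it or judges it not reportable. Symptomatic harm is also sought by neurological examination (6.6.3), physical examination (6.6.4) and leg-pain VAS (6.6.8). This stands as a reason against forced reconciliation. It is not a reason to keep recorded structural data out of the safety tables.

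Several stronger readings are tempting, and the documents do not support them:

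- *Imaging safety rests only on site reads.* Disc height in 9.7.1 contradicts this. The point holds for imaging-based adverse events.
- *Core-lab findings never reach the site.* Appendix 1 is redacted, as are contents entries after 9.7.1. A notification rule or structural safety table may be there.
- *The core lab already reads for every harm listed in 6.6.7.* The readable text gives that list to investigators. The core lab's full follow-up list cannot be seen.
- *Sites make a single read.* Section 6.6.7 mentions associated reports, so a local reader's report may sit beside the investigator's review.
- *The arms are compared with bias.* Site assessors are blinded (5.5), and nothing shows that misses differ by arm.

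**Conclusion.** The point holds as a limited improvement to a rule that the protocol states outright; it is not an error in the plan. Imaging-based safety issues and adverse events are determined from investigator reviews, reconciliation with the blinded, dual-read and adjudicated core-lab reads is waived, and core-lab results are assigned to efficacy. Beyond disc height, no core-lab structural finding is said to enter the safety evaluation.

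The conclusion rests on the readable text and on taking disc height as a core-lab measure. The size of any under-count cannot be given from the documents, and the case does not depend on one: the core-lab data already go to the sponsor or designee, so using them for safety costs little.

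**What to change.** Amend 6.6.7 and 9.7.1 so that new or worse structural findings at the treated and adjacent levels, where the core lab already records them at follow-up, are tabulated by arm in the safety analysis beside investigator-reported imaging events. Give the same table to the DSMB. State in 9.7.1 which read supplies disc height and the reported imaging events.

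Limit the table to what Appendix 1 already has the core lab record, so that no additional reads are required. Full reconciliation is not needed, and the efficacy reads do not change.

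Optionally, unless Appendix 1 already provides for it, add a treatment-blind notice of such findings to the medical monitor and investigator, with the investigator documenting the adverse-event decision. This part is more debatable. It creates site work on incidental findings, and it could influence later patient-reported outcomes or intervention decisions before Visit 8, both of which feed the primary endpoint. The tabulation has neither drawback and costs one extra table.
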